5. SUMMARY

5.1. *Identification of the promoter*

Sexological Institute of Murcia (ISM)
[name]
Teléfono: [name]
N.I.F [name]

5.2. **Title of Clinical Trial**

A randomized closed trial (RCT) to compare the effectiveness and safety of a masturbation aid's exercise protocol as a first-line treatment for patients with primary premature ejaculation.

5.3. **Protocol ID Code**

Protocol ID Code: ISM-SCT-2019-01

5.4. **Lead Researcher**

[name]
Director, Sexological Institute of
Murcia
[name]

5.5. **Location of trial**

The trial will be conducted in the following Clinic:

1. Sexological Insitute of Murcia
[name]
[name]. [contact]
18 RES: 40002570

5.6. **Ethics committee and participating clinics.**

This trial has been submitted for the approval of the Ethics Committee in the following establishment:

- Hospital José M^a Morales Meseguer – Murcia

The following clinics will take part in the trial:

- Sexological Institute of Murcia, Spain

5.7. **Main objective**

Assess the effectiveness of a cognitive-behavioral program called Sphincter Control Training (SCT), within an app for android systems, as treatment of primary premature ejaculation in Spanish population and determine if said program is enhanced with the use of a device to help masturbation specially designed for the same..

5.8. **Design**

-This research project will use two experimental groups. One will be given the "SCT" therapy on its own (experimental group 1) and the other will be given the "SCT" therapy combined with the aforementioned device (experimental group 2). The subjects in both groups will experience parallel therapy with the same exercise protocol (with the only difference being that, in experimental group 2, the SCT exercises will be carried out with the device in question). The participants who meet the selection criteria will be randomly assigned an experimental group, along with its corresponding conditions.

5.9. **Illness or condition under investigation**

Primary Premature Ejaculation (F52.4).

5.10. *Information regarding the device under investigation and the exercise program.*

Device under investigation: Myhixel I.

Dimensions

Length: 4,45 Inches (113 mm)

Width: 4,45 Inches (113 mm)

Height: 8 Inches (203 mm)

Diameter 3,58 Inches (91mm)

Weight 22,22 Oz (630 grams) with lid

19,75 Oz (560 grams) while using

Materials

Thermoplastic Elestomer

[figure not shown]
ABS

Silicone

Type of Battery Lithium

Charger Type USB + Magnet (Waterproof)

DATA SHEET ANNEXED 2

Exercise program: SCT.

The home exercise program includes 4 activities:

The first exercise called "Discovering your pelvic floor" will be carried out for one week, the second, called "Stop and Start", should be carried out for 3 weeks. The third is called "Stop and Start constant stimulation" and should be carried out for 2 weeks, and the last exercise in the program, "Stop and Start, constant stimulation with coital movements" will be carried out for a week.

Exercise information APPENDIX 3

Lubricant to be used in the trial: Myhixel lube.

Content: 50 ml (1.69 Oz)

Ingredients: Water, Propylene Glycol Hydroxycyclulose, Sodium Benzoate, Polysorbate 20, Potassium Sorbate, D-limonene, Sodium Hydroxide, Carica Papaya

Fruit Extract, Chamomilla Recutita, Flower Extract, Citric Acid, Plankton Extract, Perfume, Sodium Citrate, Citral, Soluble Collagen.

5.11. **Sample group and number of participants.**

The sample group will be heterosexual men, aged 18 or older, taken from all over the country. They all suffer from primary premature ejaculation, haven't received any treatment for the condition in the past, and have had a stable partner for at least 3 months before the start of the trial.

A sample size of 50 patients is expected. We estimate a 30% dropout or non-compliance during the study.

5.12 **Schedule and proposed end date**

Duration of the inclusion period: June 2019 - August 2019

Planned trial start date: July 2017

Planned trial end date: September 2017

5.13. **Financing**

Funding will be provided by the research area of the Sexological Institute, Murcia, Spain, and the NEW WELLNESS CONCEPT SL.

6. **RELEVANT FINANCIAL ASPECTS OF THE TRIAL**

50% of the project's funding will be provided by the research area of the Sexological Institute, Murcia, Spain, while the other 50% will be funded by the NEW WELLNESS CONCEPT SL.

This 50 % includes the provision of 30 Myhixel I devices and 30 bottle of lubricant Myhixel lube.

FINANCIAL REPORT ON THE PROJECTED EXPENDITURE OF THE RESEARCH PROJECT:

Title: **PROTOCOL INVESTIGATION: MYHIXEL**

Research code: **ISM-SCT-2019-01**

Lead Researcher: **[name]**

Promoter: **Sexological Institute, Murcia, Spain**

DETAILED DESCRIPTION OF PROJECTED FUNDED COSTS

COSTS PERSONNEL:	
1 Part-time Research Intern	400,00 €/month *
SUBTOTAL PERSONNEL:	1.200 ,00 €
FACILITIES, MATERIALS, SOFTWARE LICENSES AND TESTS:	
Licenses and correction kit MCMI-III, PEP, PEDT y GRISS male.	66,49 €
1 monthly license IBM SPSS statistics software.	88,50 €
MRW Courier Service ecommerce National Transport 30 kits	275,10 €
SUBTOTAL FACILITIES AND EQUIPMENT:	430,09 €
CONSUMIBLES:	
50 Myhixel lubricant (HOLE LOTION)	480,00 €
30 Myhixel Device	990,00€
SUBTOTAL CONSUMIBLES:	1470,00€

OTHER COSTS: (specify details of costs and amounts paid)	
Domain and hosting, web landing page for trial, yocontrolo.org, Arsys S.L.U.	101,41€
Online templates Web Templates Ltd	67,00 €
SUBTOTAL OTHER COSTS:	2043,91 €
TOTAL PROJECT BUDGET:	5.419,10 €

8. JUSTIFICATION AND RELEVANCE OF THE TEST

Premature ejaculation (PE), understood as a lack of ejaculatory control accompanied by short (up to one minute) intravaginal ejaculatory latency (IELT) times, with minimal stimulation and before the individual desires it (Serefoglu et al., 2014). It is considered the most common male sexual dysfunction, affecting millions of men worldwide (Russo et al., 2016). Treatments for PE currently include a combination of drugs and sexual or psychological therapies, and, in particular, behavioral techniques for the man and his partner.

The psychological theories attempt to explain the etiology of PE from a point of view that includes the effect of early experience and sexual conditioning, anxiety, sexual technique, frequency of sexual activity, and psychodynamic explanations of development (e.g., Brody & Weiss, 2015). However, the biological theories have the most scientific evidence (e.g., Waldinger, 2002, Corona et al., 2008). Among these, the classic model explains the process of human ejaculation in which the emission, which forms a "pressure chamber" (created in the prostatic urethra), is followed by the expulsion (rhythmic contractions in the penile smooth muscle) of the seminal fluid (Marberger, 1974).

Although new and often better-selling drug therapies are overshadowing traditional psychological and behavioral methods in the treatment of PE, there is currently no evidence to show that there is only one physiological cause underlying PE (Althof et al., 2014). Furthermore, psychological strategies based on behavioral techniques for the treatment of PE have been shown to have had some success in alleviating this dysfunction (Althof et al., 2006).

Only a few studies have compared PE psychotherapeutic techniques, either against a control condition (currently on a waiting list) or against other psychological treatment. The lack of specific treatment protocols and research funds to conduct well-designed testing studies of these protocols has diminished the attractiveness of these approaches with respect to evolving pharmacological strategies.

This is despite the fact that several cognitive-behavioral strategies come close to meeting the criteria for empirical support.

Among them is the "start-stop" method, developed by Semans (1956) and adapted by other authors such as Glina et al (2007), which suppresses the urge to ejaculate by stopping or pausing sexual stimulation before reaching the point of imminent ejaculation by means of a "glans grip". In addition, we know that the use of external devices can be effective in helping to control ejaculation (Rodriguez & Lopez, 2016).

This project aims to demonstrate the efficacy of Semans' adapted "start-stop" combination treatment on PE (1956) as part of an exercise program carried out with an external device similar to that used in Rodriguez & Lopez's research (2016). The study aims to provide scientific and methodological evidence for a cognitive-behavioral treatment that offers an alternative to current pharmacological treatments for PE.

9. DESIGN AND RATIONALE

In both groups, and to enable both groups of subjects to access treatment for PE, the control will be intra-subject. The main variables and data to establish the baseline of each group will be collected during a period of a similar length to the treatment period.

-This research project will use two experimental groups. One will be given the "sct" therapy (experimental group 1) and the other will be given the "start-stop" therapy combined with the external device (experimental group 2). The two groups will receive parallel therapy with the same exercise protocol (with the only difference being that, in experimental group 2, the sct exercises will be carried out with the device in question). The participants who meet the selection criteria will be randomly assigned to an experimental group, along with its corresponding conditions.

10. MAIN OBJECTIVE

The aim of the project is to demonstrate the effectiveness on PE of the "sct" combination treatment adapted from Semans (1956) within the framework of an exercise program carried out with an new external device specific design for this method .

Its effectiveness on PE will be reflected in increased intravaginal ejaculation latency times (IELT) and subjective perception scores from baseline therapy. The increased efficacy of the combination therapy ("sct" in conjunction with external device) will be reflected in the greater increase in IELT and subjective perception scores from combination therapy over "sct" therapy. The level of scientific evidence will indicate the competitiveness and efficacy of this cognitive-behavioral psychological technique.

11. MAIN EVALUATION PARAMETER

The main evaluation parameter is the intravaginal ejaculation latency time (IELT). This is a variable that is calculated by the experimental subject himself, and is the time, in seconds, from when penetration begins until ejaculation. It is the most studied variable in research of this type (Waldinger, Zwinderman, Olivier, & Schweitzer, 2008).

Other variables taken into account are of a more psychological nature and reported by the patients themselves. On the one hand, the subjects' perception of their own ejaculation: the personal stress it causes them, their satisfaction with sexual activity/intercourse and any interpersonal difficulties relating to ejaculation. On the other hand, there are variables related to sexual satisfaction such as the patient's perception of impotence, perception of premature ejaculation, avoidance of sexual activity/intercourse, lack of sensuality, and level of satisfaction/dissatisfaction with sexual activity/intercourse.

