13. PATIENT INCLUSION AND EXCLUSION CRITERION

Inclusion criteria for selection will be: aged 18 or over, in a heterosexual relationship for at least the last 6 months, having a score greater than 11 on the PEDT (Premature Ejaculation Diagnostic Tool) and a mean self-reported IELT (Intravaginal Ejaculatory Latency Time) of <120 seconds.

Exclusion criteria will include: History of alcohol abuse or dependence, having received medication or psychological treatment for PE in the last 3 months, having diabetes, or a regular use of recreational drugs (except tobacco and caffeine).

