14. STATISTICAL ANALYSIS

As the main evaluation parameter, the "fold change" of the IELT will be used, which will be calculated using the geometric averages of the post-treatment IELT (period B) divided by the average of the IELT at the beginning of the treatment that served as a baseline (period A).

The Mahalanobis distance test will be used to check the existence of outliers (with a Z score of > 3) and the Kolmogorov-Smirnov test to check the goodness of fit of the data and the Square Root Transformation in those cases where the assumption of normality is not met.

The Greenhouse-Geisser method will be used to correct for degrees of freedom when the sphericity assumption is not met.

The MANOVA contrast will be performed for the demographic variables, and, presumably, we will find significant differences in variables such as age.

For the contrasts, ANCOVAs of independent measurements will be used, with the variables that have come out as significant in the MANOVA contrast as covariates, to check the differences between the two experimental groups and the equality between baselines in each of the study variables. And, similarly, ANCOVAs of repeated measurements to check the existence of the benefits of each therapy on the baseline.

All p values should be bilateral and the significance level used < 0.05. The IBM SPSS Statistics version 22 statistical package should be used.

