19. INTERVIEWS, QUESTIONNAIRES OR INSTRUMENTS TO BE USED IN THE TRIAL

The IELT measurements will be collected by self-registration after each week of treatment (APPENDIX I).

In order to collect the information regarding the perception of ejaculation, the Premature Ejaculation Profile (PEP) will be used (Patrick et al., 2009), a self-reported instrument consisting of four measurements (perceived control over ejaculation, personal stress related to ejaculation, satisfaction with sexual relationships, and interpersonal difficulty related to ejaculation). These will give an overall profile and score (Patrick et al., 2009), where the lowest scores express the lowest performance. The reliability coefficient between ranges from 0.66 to 0.83 and its validity was contrasted with dapoxetine and Intravaginal Ejaculation Latency Times (IELT). This instrument was validated in American and European trials, with people from Germany, France, England, Italy and Poland involved (Giuliano et al., 2008) although it has been used also in the Spanish community (Bar-Or, Salottolo, Orlando, Winkler, & Group, 2012; Buvat, Tesfaye, Rothman, Rivas, & Giuliano, 2009).

The Premature Ejaculation Diagnostic Tool (PEDT) will be used for the diagnosis. It takes five measurements in order to evaluate difficulty in delaying the ejaculation, ejaculation occurring before the patient wanted it, ejaculation with little stimulation, frustration related to premature ejaculation, and the couple's opinion about ejaculation. The test-retest reliability is 0.82 and all values statistically distinguish and differentiate statistically between PE and non-PE patients.

The Golombok-Rust Inventory of Sexual Satisfaction (GRISS) will also be applied. This is a brief 28-question questionnaire to assess the existence and severity of sexual problems in both members of a heterosexual relationship (Rust & Golombok, 1985, 1986). This questionnaire provides separate scores for men and women on 3 shared scales (avoidance, non-sensitivity, and dissatisfaction) and 6 gender-specific scales (impotence, premature ejaculation, anorgasmia, vaginismus, infrequency, and lack of communication) with acceptable values of reliability and validity (Rust & Golombok, 1985, 1986). The instrument was validated in the English community and is already being used in Spain in the official Master's degree in Sexology at the University of Almeria (García González, 2013; López Lorente, 2013).

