Waldinger, M. D., Zwinderman, A. H., Olivier, B., & Schweitzer, D. H. (2008). Geometric Mean IELT and Premature Ejaculation: Appropriate Statistics to Avoid Overestimation of Treatment Efficacy. *The Journal of Sexual Medicine*, 5(2), 492–499

Collaborator's signature:
Instituto Sexológico Murciano

INSTITUTO SEXOLOGICO MURCIANO
N.R.S 20300055
[contact]
www.isemu.es | [contact]

Lead Researcher's signature
[name]

Annexed 1

Data collection forms

REGISTER OF EJACULATION TIMES

[figure not shown]
[figure not shown]
[figure not shown]
[figure not shown]
[figure not shown]
[figure not shown]
[figure not shown]
[figure not shown]
[figure not shown]
[figure not shown]
[figure not shown]
[figure not shown]

[figure not shown]
WEEK:

NAME:

MONDAY TUESDAY WEDNESDAY THURSDAY FRIDAY SATURDAY SUNDAY

[figure not shown]
[figure not shown]

[figure not shown]

[figure not shown]
[figure not shown]
[figure not shown]
[figure not shown]
[figure not shown]
[figure not shown]

MASTURBATION

Record the time you take to ejaculate when masturbating

[figure not shown]
PENETRATION INTERCOURSE

Record the time you take to ejaculate after penetration

Annexed 2

ANEXO 2

[figure not shown]

PARTES.

1 – Pines magnéticos de carga

2 – Rosca hembra para aplique de manos libres.

- 3 – Rosca reguladora de succión.
- 4 - Botonera para control de vibración y calefacción.
- 5 – Conexión con resistencia calefactora
- 6 – Orificio de entrada de la manga
- 7 – Motor vibrador
- 8 – Bolsillo para albergar el motor vibrador.
- 9 – Palo calefactor.
- 10 y 11 – Sistema de imanes para asegurar el cierre.

**DIMENSIONES
PRINCIPALES**

MATERIALES Y PESO

PARTE	MATERIAL
MANGA	TPE (Elastómero termoplástico)
CUERPO	ABS
PALO CALEFACTOR	
RECUBRIMIENTO DEL CUERPO "SOFT TOUCH"	PDMS ("Silicona soft touch")

[figure not shown]
PARTE	PESO (gramos)
MANGA	340
MYHIXEL I (con manga)	670

MYHIXEL I (en uso, sin calefactor)	560
------------------------------------	-----

ELECTRONICA Y FUNCIONES

PARTE	MATERIAL
BATERÍA	POLÍMERO DE LITIO (650 Ma 3.7 V)
MOTOR VIBRADOR	~2 V (3.5 mm y 100 HZ)
CALEFACCIÓN	RESISTENCIA EN POLIAMIDA
CARGA	PINS MAGNÉTICOS + USB

1	2	3	4	5	6
LED 1+2	LED 1+2	LED 1+2	LED 1	LED 1	LED 2
CARGANDO	CARGADO	BATERÍA BAJA	CALENTANDO	TEMPERATURA ALCANZADA	VIBRACIÓN
Leds ON fijo	Leds OFF	Los leds parpadean alternativamente	Led ON Latente (ver link adjunto)	Led OFF	Led On Durante 10 sg y luego OFF

COLOR LEDS (1 y 2): **BLANCO CÁLIDO**

APPENDIX 3

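### The primary endpoint is timed by unblinded men themselves, and the protocol names no timing method and no common method for the two periods of the fold change

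*Protocol*

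**What the plan says.** Section 11 says of the main parameter: "This is a variable that is calculated by the experimental subject himself". It is expressed in seconds and runs from the start of penetration to ejaculation. This fixes the start, the end and the unit, but not the means of measurement.

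Section 19 describes collection: "The IELT measurements will be collected by self-registration after each week of treatment". It points to the register in Annex 1, which has one column per day ("MONDAY TUESDAY WEDNESDAY THURSDAY FRIDAY SATURDAY SUNDAY") and gives the instruction "Record the time you take to ejaculate after penetration".

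Section 13 admits men with "a mean self-reported IELT (Intravaginal Ejaculatory Latency Time) of <120 seconds". That is an entry limit and does not cap follow-up values.

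Section 14 makes the fold change of IELT the main evaluation parameter: the geometric average in period B over the average in period A. Section 9 says that control is within the subject and that baseline data come from a period about as long as treatment. Section 19 mentions self-registration only for treatment weeks, and no section says how baseline times are obtained.

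Sections 5.8 and 9 state that the arms differ only in use of the device. No blinding is described.

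**The concern.** A latency of a minute or so is hard to judge without a clock. A man who estimates is likely to round, and rounding is coarsest in relative terms where times are shortest, which is at baseline. A ratio endpoint carries such error directly.

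Two different harms are possible:

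- **Random or rounding error common to both arms.** This costs precision and can shrink the fold change. It does not create a difference between arms when there is none.
- **Error that differs between periods or arms.** A shift between periods A and B biases the within-subject comparison. A shift in one arm only, for instance because men with the device expect more of it, biases the randomised comparison.

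The protocol leaves both open. How the primary endpoint is measured belongs in Sections 11 and 19 and on the register. Those places do address it, but they leave the means to each man.

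**Working it through.** The protocol gives no error size, target effect or SD, so every error, SD and bias value here is an assumption.

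**1. The plan's own figure.** Section 12 states 24 per group, power 0.80 and alpha 0.05; Section 14 makes tests two-sided. The 24 cannot be reproduced without an effect size, but it can be inverted:

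d = (1.960 + 0.842) × √(2/24) = 0.81.

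On the log scale the between-arm ratio sought is exp(d × SD):

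| Assumed SD of log fold change | Implied ratio |
|---|---|
| 0.4 | 1.38 |
| 0.6 | 1.62 |
| 0.8 | 1.91 |
| 1.0 | 2.25 |

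**2. Rounding, same method in both periods.** Assume true baseline IELT is log-normal with median 45 s and log-SD 0.6, truncated at the 120 s entry limit (200,000 draws). Let every man truly double his time. Round both values to the nearest unit, with one unit as the minimum, and take the geometric mean of the ratios:

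| Rounding unit | Observed fold change (true 2.0) |
|---|---|
| 5, 10 or 15 s | 2.00 to 2.01 |
| 30 s | 1.88 |
| 60 s | 1.41 |

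At baseline, 30 s rounding multiplies the geometric mean by 1.06 and adds a log-error SD of 0.28 per record. For 60 s rounding the figures are 1.50 and 0.48. Averaging several records lowers the error SD but does not remove the shift.

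**3. Random error and power.** Take d = 0.81 as the error-free effect, so that the observed effect is d × √reliability. With 24 per arm, power falls from 0.80 to 0.76, 0.71, 0.65 and 0.51 at reliability 0.9, 0.8, 0.7 and 0.5.

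**4. Expectation bias in the device arm only, with no true effect.** With over-reporting ratio b, the shift in standard-error units is ln(b) / (SD × √(2/24)). For b = 1.2 and SD = 0.4 this is 0.1823 / (0.4 × 0.2887) = 1.58. The two-sided rejection rate is then Φ(1.58 − 1.96) + Φ(−1.58 − 1.96) = 0.35. Repeating this:

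| SD of log fold change | 20% over-reporting | 30% over-reporting |
|---|---|---|
| 0.4 | 0.35 | 0.62 |
| 0.6 | 0.18 | 0.33 |
| 0.8 | 0.12 | 0.21 |
| 1.0 | 0.10 | 0.15 |

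The nominal rate is 0.05.

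**The case against.** The definition has a start, an end and a unit of seconds, and the form asks for a time on each day. The natural reading is daily entries handed in weekly. In a translated document, calculating need not mean guessing. Several Annex 1 figures are not shown, so a timing instruction may be there. All this stands: timing is unspecified, not excluded, and a reader should not infer that the protocol forgoes timed measurement.

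A reader might also infer that screening guesses and timed acts end up in the same ratio. The documents do not support that. Section 9 describes a separate baseline period, and the 120 s figure is an eligibility rule. Nothing says that it serves as period A.

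The rounding distortion is modest unless men round to whole minutes, and it works against showing benefit. The bias between arms is assumed, not demonstrated. Group 1 also receives an active programme, so the gap in expectation may be smaller than against no treatment. These limits on size are fair.

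Finally, a stopwatch held by the same unblinded man is still self-report. That is true, but a timer reading leaves less to judgement than an estimate, and a common method closes off drift between periods.

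**Conclusion.** The point holds in a limited form. The primary endpoint is self-measured by men who know their arm, and the readable protocol fixes neither a timing method nor a common method for periods A and B.

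Under the assumptions above, whole-minute rounding in both periods would turn a true doubling into about 1.4-fold, while rounding to 15 s or finer would do almost nothing. Over-reporting of 20% in the device arm alone would raise the false-positive rate to 0.10 for a log fold-change SD of 1.0, and to 0.35 for an SD of 0.4.

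It would be tempting to say that the error matches the effect the trial seeks. The documents do not support that, because no target effect or SD is stated. The ratio implied by 24 per group, 1.38 to 2.25, exceeds a reporting bias of 1.2 or 1.3 across the assumed SDs. Such a bias can mislead without being that large.

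This should be changed: the weakness is in the main endpoint and the remedy is cheap.

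**What to change.** In Sections 11 and 19 and in Annex 1:

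- Define IELT as the reading of a stopwatch or phone timer, started at penetration and stopped at ejaculation.
- Have each reading entered in that day's column of the register on the same day.
- State that periods A and B use the same method and the same register.
- State that the self-reported figure in Section 13 serves eligibility only and is never used as period A.

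The cost is a few lines of wording and one instruction on the register. The programme runs in an Android app (Section 5.7), so a phone timer should be at hand and no equipment or staff are added. The downside is slight intrusiveness. Because the lack of blinding remains, it should be stated as a limitation when the comparison between arms is interpreted.
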